4. GENERAL STATISTICAL CONSIDERATIONS

4.1. Statistical Hypothesis

Due to the study termination, no formal statistical testing will be performed.

4.2. Sample Size

Based on a completed study of newly diagnosed AML subjects treated with ENTO, it is anticipated that 87% of *NPM1*-m subjects will achieve CR (Walker et al, 2020). Based on analysis of a historical dataset from the Cancer and Leukemia Group B Alliance (Mims et al, 2021) showing a 68% CR rate in 107 *NPM1*-mutated/*FLT3-ITD* negative patients \geq 60 years of age treated with 7+3 induction, a conservative estimate of 70% CR rate for placebo is assumed for sample size determination. The MRD negative rate among placebo subjects achieving CR is assumed to be 60% (Ivey et al, 2016). Alternatively, it is hypothesized that 80% of subjects with CR receiving ENTO will be MRD negative.

Approximately 180 subjects will be randomized with a randomization ratio of 1:1. A sample size of 90 subjects per group will provide $> 97\%$ power to detect a difference in the MRD negative CR rate of 28% (87% x 80% = 70% for ENTO vs 70% x 60% = 42% for placebo) with a 2-sided alpha level of 0.05 (PASS 2008: Two sample test of Proportion Module). Up to 10% over enrollment is allowed in order to account for technical or logistical barriers (e.g., inadequate bone marrow aspirate or poor sample quality) related to the ascertainment of MRD status in patients who achieve CR post-Chemotherapy Cycle 2.

Assuming the two-year event free survival (EFS) rate for the control group is 63% (hazard rate of 0.231), a total of 124 events (70 in the placebo arm, 54 in the ENTO arm) would be sufficient to provide 80% power to detect a hazard ratio of 0.6 for EFS (PASS 2008: log rank tests (Lakatos) [Hazard Rate] module) assuming 2-sided alpha = 0.05 and a total study duration of 60 months.

The study was terminated early with a final sample size of 15 randomized subjects.

4.3. Measures to Minimize Bias: Randomization and Masking

Subjects will be randomized 1:1 to study medication (ENTO or placebo) using an Interactive Voice/Web Response System (IxRS) and randomization schedule prepared by a non-study statistician using PharPoint standard operating procedure BIO002. The randomization will be stratified by age (< 60 years vs ≥ 60 years) and anthracycline administered during induction (daunorubicin or idarubicin). All subjects, study site personnel, and the Sponsor's clinical trial management staff and their designees will be blinded to treatment assignment.

Under certain circumstances, members of the DMC may be unblinded to treatment assignment for individual subjects or treatment arm, in order to better assess safety and efficacy trends that could potentially underlie the basis for specific recommendations to modify the study. The criteria and procedures for unblinding at the DMC are outlined in the DMC Charter. Investigators will also have the ability to unblind the study medication assignment for individual patients in circumstances where this

information is critical for the assessment and management of specific adverse events, including suspected, unexpected, serious adverse events (SUSARs) and Grade 5 AEs assessed as at least possibly related to study medication. The investigator will have the capability to unblind the study medication assignment for individual patients without prior authorization from the study medical monitor or Sponsor and will access this information via the IxRS. Upon unblinding the medication assignment for a specific patient, the investigator must notify the study's medical monitor as soon as possible thereafter.

4.4. Handling of Data

4.4.1. Strata and Covariates

No adjustments for strata and covariates will be implemented.

4.4.2. Examination of Subject Subsets

No planned analysis of subject subsets will be conducted.

4.4.3. Multiple Testing and Comparisons

No statistical inference is planned.

4.4.4. Definitions and Data Derivations

Age

Age is defined as the age in years at time of informed consent recorded on the Demographics page of the CRF.

Study Medication

Study medication refers to ENTO/placebo.

Study Treatment

Study treatment refers to ENTO/placebo and/or chemotherapy.

Time since AML Diagnosis

Time since AML diagnosis, expressed in weeks, will be calculated as (date of randomization – date of AML diagnosis +1)/7.

Cycle 1 Day 1 (Baseline)

Cycle 1 Day 1 (C1D1) is defined as the earliest day that the first dose of any component of study treatment is administered.

Baseline Value

Baseline value is defined as the last observation of an assessment prior to the first dose of study treatment.

Study Day

Study Day is defined relative to C1D1. For events prior to C1D1, Study Day is calculated as:

$$\text{Study Day} = \text{event date} - \text{date of C1D1}$$

For events occurring on or after C1D1, Study Day is calculated as:

$$\text{Study Day} = \text{event date} - \text{date of C1D1} + 1$$

Post-Baseline Value

Any assessment occurring after the initiation of study treatment will be considered a post-baseline value. For assessments occurring on C1D1 where no time of assessment is captured, the value will be considered as post-baseline if the assessment was not planned as part of the set of screening assessments (e.g., an assessment taken on C1D1 where no time was recorded but not designated as a screening assessment will be considered a post-baseline assessment whereas a laboratory assessment on C1D1 without a time but designated as a screening assessment will be considered as such).

Change from Baseline

Change from baseline will be determined for post-baseline assessments (where applicable) as:

$$\text{Post-baseline value} - \text{baseline value}$$

Days on Study Medication

Days on study medication is the number of days from C1D1 (or the first day of study medication, if later) to the date of the last dose of study medication as recorded on the Study treatment- Oral administration page of the CRF.

Days on Study Treatment

Days on study treatment is the number of days from the start of study treatment (either study medication or chemotherapy) to the date of the last dose of study treatment as recorded on the Study treatment- Oral administration or Study treatment- IV administration pages of the CRF.

Days on Study

Days on Study is the number of days from C1D1 to the date of completion or study discontinuation on the End of Study page of the CRF.

Cumulative Dose of ENTO

Cumulative dose of ENTO is defined as the sum of the doses administered to a patient measured in milligrams (mg). For subjects receiving placebo, this is set to 0 mg.

Cumulative Dose of Chemotherapy

The cumulative dose of each chemotherapy agent is defined as the sum of the doses administered to a patient measured in milligrams per meter squared (mg/m^2). Cumulative chemotherapy administration will be calculated separately for Induction and Consolidation.

Actual Dose Intensity (mg/m²)

The actual dose intensity will be defined separately for each chemotherapy component by phase (Induction, Consolidation) and treatment cycle (as the cumulative dose / duration).

Relative Dose Intensity

Relative dose is set to 100*(Actual Dose Intensity/ (Expected Cumulative Dose / 28)).

Completed Chemotherapy Cycle

A chemotherapy cycle is considered completed if at least one of the assigned chemotherapy agents in the regimen has been completed per protocol. Information regarding premature discontinuation of chemotherapy will be as recorded on the Study treatment – IV administration pages of the CRF.

Response Criteria

Criteria for responses as outlined below and assessed by the investigator are based on the ELN 2017 definitions (Döhner et al 2017) with minor modification for neutrophil and platelet count thresholds as defined by the IWG and as applicable to the current study:

CR*

CR requires all the following:

- Bone marrow blasts < 5%
- Absence of circulating blasts and blasts with Auer rods
- Absence of extramedullary disease (i.e., leukemia outside of bone marrow confirmed by biopsy)
- Absolute neutrophil count > 1.0 x 10⁹/L (1000/µL)
- Platelet count > 100 x 10⁹/L (100,000/µL)

*Note: *MRD positive or unknown*

Complete Response with Hematologic Improvement (CRh)**

CRh requires all the CR criteria, except for residual thrombocytopenia and/or neutropenia and is defined as:

- Bone marrow blasts < 5%
- Absence of circulating blasts and blasts with Auer rods
- Absence of extramedullary disease
- Absolute neutrophil count > 0.5 x 10⁹/L (500/µL)
- Platelet count > 50 x 10⁹/L (50,000/µL)

Complete Response with Incomplete Blood Count Recovery (CRi)**

CRi requires all the CR criteria, except for residual neutropenia or thrombocytopenia and is defined as:

- Bone marrow blasts < 5%
- Absence of circulating blasts and blasts with Auer rod
- Absence of extramedullary disease

- Absolute neutrophil count $\leq 1.0 \times 10^9/L$ (1000/ μ L) or platelet count $\leq 100 \times 10^9/L$ (100,000/ μ L)

*Note: **If subjects meet criteria for both CRh and CRi, they should be classified as CRh*

Morphologic-free Leukemia State (MLFS)***

- Bone marrow blasts < 5%
- Absence of blasts with Auer rods
- Absence of extramedullary disease
- No hematologic recovery required

*Note: ***Marrow should not be merely “aplastic”; at least 200 cells should be enumerated or cellularity on bone marrow biopsy should be at least 10% of normal.*

Partial Response (PR)

PR meets all hematologic criteria of CR:

- Absolute neutrophil count $> 1.0 \times 10^9/L$ (1000/ μ L)
- Platelet count $> 100 \times 10^9/L$ (100,000/ μ L), and
- Residual bone marrow blast percentage of 5% to 25%
- Reduction of bone marrow blast percentage by $\geq 50\%$ compared with pretreatment

Stable Disease (SD)

Absence of MRD negative CR, CR, CRh, CRi, PR, MLFS and criteria for PD not met.

Progressive Disease (PD)

Evidence for an increase in bone marrow blast percentage and/or circulating blast counts as defined by at least one of the following:

- 50% increase in bone marrow blasts over baseline (a minimal absolute 15% increase is required in cases with < 30% blasts at baseline), or
- Persistent bone marrow blast percentage $> 70\%$ over ≥ 3 months without at least a 100% improvement in ANC to an absolute level $> 0.5 \times 10^9/L$ (500/ μ L) and/or platelet count to $> 50 \times 10^9/L$ (50,000/ μ L) without transfusion, or
- 50% increase in circulating blasts to $> 25 \times 10^9/L$ ($> 25,000/\mu L$) in the absence of Differentiation Syndrome,**** or
- New extramedullary disease

**** Certain targeted therapies, for example, those inhibiting mutant isocitrate dehydrogenase (IDH) proteins, other kinase or targets may cause a transient increase in the percentage of bone marrow blasts accompanied by an increase in circulating blasts (differentiation syndrome). In the setting of therapy with such compounds, an increase in blasts may not necessarily indicate progressive disease. Such instances should be discussed with the study medical monitor on a case-by-case basis.

Recurrence

Recurrence for subjects with prior MRD-CR, morphological CR, CRh, CRi, or MLFS is defined as one of the following:

- Morphologic relapse as defined by the reappearance of circulating blasts or $\geq 5\%$ blasts in the bone marrow not attributable to any other cause. *Note: In the setting of recent treatment, if there are no circulating blasts and the bone marrow contains 5 to 20% blasts, a bone marrow aspirate/biopsy should be repeated within 1 week to distinguish relapse from bone marrow regeneration.*
- Reappearance of cytologically or biopsy documented extramedullary disease, including new CNS disease or other new sites of extramedullary involvement. *Note: The reappearance of a cytogenetic or molecular abnormality would be considered a cytogenetic or molecular relapse. In the absence of morphologic relapse, this would not be considered a recurrence.*

Evaluation of response is recorded on the Response Assessment eCRF, and documentation of recurrence (relapse) is recorded on the Relapse Assessment eCRF.

Adverse Event

An AE is defined as any untoward medical occurrence in a clinical study subject, temporally associated with the use of study treatment, whether or not considered related to the study treatment.

Treatment-emergent Adverse Event (TEAE)

A TEAE is any adverse event beginning or worsening from C1D1 through 30 days following study treatment completion.

Treatment-emergent Laboratory Toxicity (TELT)

A TELT is a laboratory abnormality as defined in the National Cancer Institute - Common Toxicity Criteria for Adverse Events (NCI-CTCAE) v5.0 (NCI 2017, which occurs on or after the start of study treatment and up to 30 days following discontinuation of all study treatment and is at least 1 grade shift from the baseline value. TELTs are determined programmatically from laboratory assessments recorded in the relevant CRF pages.

Concomitant Medications

Concomitant medications are those medications taken on or after the initiation of study treatment. This includes medications started prior to the initiation of ENTO/placebo and continued after the initiation of ENTO/placebo. These medications will be recorded in the Prior and Concomitant Medications page of the CRF.

Prior Medications

Prior medications are those medications taken and discontinued prior to the initiation of study treatment. These medications will be recorded in the Prior and Concomitant Medications page of the CRF.

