6.4 Compliance with Study Medication Regimen

Compliance with the study medication dosing schedule will be documented at each study visit via diary cards placed in the subject's medical record and entered in the electronic case report form (eCRF) at each scheduled visit. Deviation(s) from the prescribed dosing schedule will be recorded.

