6.3. Exposure to Treatment

The number of days on oral study drug and cumulative dose will be summarized by treatment group for the Safety Analysis Set. Additionally, the number of chemotherapy cycles completed and the relative dose intensities for each chemotherapy agent will be presented by treatment group, separately for Induction and Consolidation and presented by cycle and overall. Drug administration details will be listed.

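### The exposure table cannot compare delivery of blinded oral study medication between arms, because placebo dose is fixed at 0 mg and interrupted days count as treated days

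*SAP*

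**What the plan says.** SAP 4.4.4 defines the dose measure: "Cumulative dose of ENTO is defined as the sum of the doses administered to a patient measured in milligrams (mg"). It then adds: "For subjects receiving placebo, this is set to 0 mg".

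The duration measure in the same section begins: "Days on study medication is the number of days from C1D1 (or the first day of study medication, if later"), and ends: "to the date of the last dose of study medication as recorded on the Study treatment- Oral administration page of the CRF". Nothing is subtracted for days off drug.

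SAP 6.3 names these two as the oral measures to be tabulated: "The number of days on oral study drug and cumulative dose will be summarized by treatment group for the Safety Analysis Set". For the background regimen it goes further: "the relative dose intensities for each chemotherapy agent will be presented by treatment group". The underlying definition covers chemotherapy only: "The actual dose intensity will be defined separately for each chemotherapy component by phase (Induction, Consolidation) and treatment cycle".

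Protocol 6.5.1 and Table 6 provide for interruptions and half-dose restarts of study medication, and because treatment is blinded these apply in both arms. Protocol 6.4 has dosing recorded: "Compliance with the study medication dosing schedule will be documented at each study visit via diary cards". It sends this to the eCRF and requires deviations from the dosing schedule to be recorded. Protocol 6.2 gives a 200 mg ENTO tablet and a matching placebo tablet.

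**The concern.** After early termination, this SAP serves an abbreviated report whose analyses are about safety. A reader comparing adverse events by arm needs to know how much study medication each arm took, and whether ENTO was interrupted or reduced more than placebo on the same chemotherapy. The oral rows of Table 3 do not answer this. The mg row compares a positive number with a zero set by definition. The days row compares calendar spans in which a day off drug counts the same as a day at full dose. Relative dose intensity, which would answer the question, is planned for every chemotherapy agent but not for the blinded product under test.

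**Working it through.** The point concerns derivation rules, so the plan has no figure of its own to reproduce. I applied the SAP definitions to example dosing records.

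**Inputs from the documents**
- Full dose: 400 mg twice daily (Protocol 6.1) = 800 mg per day. With 200 mg tablets (Protocol 6.2), that is 4 tablets per day.
- Half dose twice daily (Protocol 6.5.1, Table 6) = 400 mg, or 2 tablets, per day.
- Span: 118 days. This is the median ENTO exposure in the earlier cohort described in Protocol 2.4, borrowed only as a plausible length.

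**Assumed inputs**
- Days off drug and days at half dose. The documents give none, so a range is shown.

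**Formulas**
- SAP days = span from first to last dose.
- SAP cumulative dose = sum of mg for ENTO; 0 for placebo.
- Tablets taken = 4 × (span − days off − days at half dose) + 2 × days at half dose.
- Percentage of planned = tablets taken / (4 × span). Planned tablets = 4 × 118 = 472.

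| Days off | Days at half dose | Tablets taken | % of planned | Days dosed | SAP days (either arm) | SAP mg, ENTO | SAP mg, placebo |
|---|---|---|---|---|---|---|---|
| 0 | 0 | 472 | 100 | 118 | 118 | 94,400 | 0 |
| 14 | 14 | 388 | 82.2 | 104 | 118 | 77,600 | 0 |
| 28 | 14 | 332 | 70.3 | 90 | 118 | 66,400 | 0 |
| 42 | 28 | 248 | 52.5 | 76 | 118 | 49,600 | 0 |

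Last row in full: 4 × (118 − 42 − 28) + 2 × 28 = 192 + 56 = 248 tablets; 248 / 472 = 52.5%; 248 × 200 = 49,600 mg.

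**Reading the table**
- A placebo subject's pair of values is 118 days and 0 mg in every row. It depends only on the first and last dose dates.
- An ENTO subject's days are equally unchanged, but the mg falls, so reduced delivery can be recovered: 49,600 / (118 × 800) = 52.5%.
- Table 3 therefore carries information on delivery in one arm only. The between-arm contrast in mg is fixed by definition, and the contrast in days reflects time from first to last dose.

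**The case against.** **Zero is the true value.** The variable is the dose of ENTO, and a placebo recipient receives none. This stands. The rule is not an error; what is missing is a parallel measure of study medication delivered, whatever the bottle contained.

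**Placebo dosing is reported elsewhere.** A reader might infer that placebo dosing records are collected and then thrown away. They are not. SAP 6 puts all collected data into listings, SAP 6.3 lists administration details, and Listing 5.2 covers oral dosing with no restriction to one arm. The gap is in tabulation.

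**There is a comparator for dose changes.** A reader might also infer that nothing in the report compares dose changes by arm. SAP 6.5.1 plans summaries of treatment-emergent adverse events leading to reduction, interruption or discontinuation of ENTO/placebo, and SAP 6 summarises discontinuation from study drug with its main reason. These cover much of the tolerability question. They do not cover doses missed for other reasons or time spent off drug, and the dose-change summaries have no separate entry in the SAP Section 10 output list.

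**A tablet ratio assigns no cause.** It is tempting to say that the added measure would separate doses missed because of chemotherapy from doses missed because of ENTO. It would not. It carries no reason for any missed dose, and a difference between arms in so few subjects could not settle the matter.

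**The consequence is small.** Fifteen subjects were randomised, no testing is planned, and a listing of that size can be read by hand. This stands and sets the severity.

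**Conclusion.** The point holds for Table 3 only. As defined, the table cannot show whether blinded study medication was delivered equally in the two arms: placebo subjects with the same dose dates get the same values whether, in the illustration, 100% or 52.5% of tablets were taken. It does not extend to the report as a whole, for the reasons given under the objection.

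Severity is low. At most 15 subjects are affected, and no estimate or decision in the plan would change. It is still worth correcting, because exposure by arm is the background against which a safety report's adverse event rates are read.

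Two assumptions matter. The interruption and half-dose lengths are invented for illustration. The claim that interrupted days are counted follows from the first-to-last-dose definition; the SAP does not say so in words.

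**What to change.** Keep cumulative ENTO in mg, shown for the ENTO arm. Add to Table 3, for both arms:
- tablets taken (200 mg or matching placebo) as a percentage of planned, with planned defined as 4 per day over the span from first to last dose, so that reductions as well as gaps show;
- days dosed, excluding interruptions;
- number and duration of interruptions and of reductions.

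State in SAP 4.4.4 that days on study medication is a span that includes interruptions.

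Derive the new rows from the oral-administration eCRF data. Check them against drug accountability records where subject-level counts exist. Protocol 6.2 requires accountability and reconciliation but does not specify returned-tablet counts by subject, so this check may not be possible for everyone.

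The cost is a few derivations, a few lines of SAP text and some extra table rows. Protocol 6.4 already requires the dosing data to be entered in the eCRF, so no new collection should be needed, provided that the form holds doses in a countable form. The form itself is not among the documents, so this should be confirmed first.

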2.1. Study Overview

This is a Phase 3, multi-center, international, double-blind, placebo-controlled study in previously untreated subjects with Acute Myeloid Leukemia (AML) harboring *nucleophosmin-1 (NPM1)* mutations. Subjects will be randomized 1:1 to receive intensive induction chemotherapy in combination with either the spleen tyrosine kinase (SYK) inhibitor, entospletinib (ENTO), or placebo. Randomization will be stratified by age (<60 or \geq 60 years) and anthracycline administered during induction (daunorubicin vs idarubicin). The study will consist of Screening, Induction, Consolidation, End-of-Treatment, and Long-term Follow-up phases.

ENTO (400 mg) or placebo will be administered continuously twice daily (BID) approximately every 12 hours beginning on Cycle 1 Day 1 of induction chemotherapy (**Table 1**) through completion of consolidation (**Table 2**), including while awaiting blood count recovery.

Subjects will undergo bone marrow examination no later than Day 42 of Induction Cycle 1 for assessment of response. Subjects with \geq 5% residual leukemic blasts in bone marrow will receive Induction Cycle 2 as outlined in **Table 1**, which may be administered prior to blood count recovery. Subjects with <5% residual blasts will receive Consolidation Cycle 1 as outlined in **Table 2** upon recovery of peripheral blood counts (absolute neutrophil count [ANC] $>$ 1.0 \times 10⁹/L; platelet count $>$ 100 \times 10⁹/L).

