After completion of Induction Cycle 2 or Consolidation Cycle 1 (hereafter referred to collectively as Chemotherapy Cycle 2), subjects will undergo bone marrow aspiration for assessment of remission status at the investigative site. Bone marrow examination should await recovery of ANC to at least 1.0 \times 10⁹/L and platelet count to at least 100 \times 10⁹/L on or before but no later than Day 42 of Chemotherapy Cycle 2 unless leukemic progression is suspected. Subjects who achieve or remain in morphologic complete response (CR) after Chemotherapy Cycle 2 will undergo measurable residual disease (MRD) assessment in peripheral blood and bone marrow aspirate. Subjects who have not achieved morphologic CR last cycle of induction chemotherapy (no later than Day 42 of the last cycle of induction) will be considered treatment failures. *For subjects with < 5% residual blasts post-Induction Cycle 1, Consolidation Cycle 1 will consist of Chemotherapy Cycle 2. For patients with \geq 5% residual blasts post-Induction Cycle 1, Induction Cycle 2 (**Table 1**) will consist of

Chemotherapy Cycle 2 with consolidation beginning thereafter. All subjects are eligible to receive up to 3 cycles of high dose cytarabine after Chemotherapy Cycle 2.

Figure 1 provides a schematic representation of the study treatment plan from Cycle 1 Day 1 through completion of Chemotherapy Cycle 2

Table 1: Induction Chemotherapy

	Age < 60 years	Age ≥ 60 years
Cycle 1:		
Cytarabine ^a	100 mg/m ² by continuous infusion, Days 1-7	100 mg/m ² by continuous infusion, Days 1-7
Anthracycline	Daunorubicin, 60 mg/m ² slow IV push, Days 1-3 OR Idarubicin, 12 mg/m ² slow IV push, Days 1-3	Daunorubicin, 60 mg/m ² by slow IV push, Days 1-3 OR Idarubicin, 12 mg/m ² slow IV push, Days 1-3
Cycle 2:		
Cytarabine	1.0 g/m ² , BID Days 1-6	1.0 g/m ² , BID Days 1-6
Anthracycline	Daunorubicin, 60 mg/m ² slow IV push, Days 1-3 OR Idarubicin, 12 mg/m ² slow IV push, Days 1-3	N/A

Abbreviations: BID, twice daily; IV, intravenous; N/A, not administered.

^a Subjects who are candidates for continuous infusion of cytarabine in Cycle 1 at doses higher than 100 mg/m²/day are ineligible.

Subjects who achieve MRD negative CR status post-induction will undergo retrospective MRD assessments in peripheral blood every 3 months until morphologic relapse.

[figure not shown]

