All subjects who achieve morphologic CR, complete response with hematologic improvement (CRh), or complete response with incomplete blood count recovery (CRI) upon completion of Chemotherapy Cycle 2 may initiate or continue consolidation therapy in combination with ENTO or placebo as outlined in Table 2 at the investigator's discretion either instead of or as a bridge to hematopoietic stem cell transplant (HSCT).

Table 2: Treatment Phase - Consolidation

	Age < 60 years	Age \geq 60 years
Cytarabine	3.0 g/m ² , BID over 3 hours on Days 1, 3 and 5 every 28-35 days for up to 3 cycles*	1.5 g/m ² , BID over 3 hours on Days 1, 3 and 5 every 28-35 days for up to 3 cycles*

*For subjects with < 5% residual blasts post-Induction Cycle 1, Consolidation Cycle 1 will consist of Chemotherapy Cycle 2. For patients with \geq 5% residual blasts post-Induction Cycle 1, Induction Cycle 2 (Table 1) will consist of Chemotherapy Cycle 2 with consolidation beginning thereafter. All subjects are eligible to receive up to 3 cycles of high dose cytarabine after Chemotherapy Cycle 2.

Figure 1: Treatment Phase- Cycle 1, Day 1 through Completion of Chemotherapy Cycle 2:

* Following recovery of ANC to $>1.0 \times 10^9 /L$ and platelet count to $>100 \times 10^9 /L$
BMA, bone marrow aspirate; MRD, measurable residual disease

Following completion of consolidation chemotherapy, all subjects will undergo an End-of-Study Treatment Visit 30 ± 7 days after the last study treatment (either ENTO/placebo or cytarabine, whichever is later) or prior to initiation of follow-on therapy (e.g., maintenance therapy, HSCT) if sooner than 30 ± 7 days after last study treatment.

All subjects regardless of their post-remission status will be followed monthly for 3 months after the End-of-Treatment Visit and thereafter at least once every 3 months for progression/relapse, first salvage therapy, and survival until study termination. Unscheduled study visits at other time points

are permitted in the setting of suspected leukemic recurrence or for evaluation and management of post-treatment sequelae.

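### The SAP's relative dose intensity sets an undefined duration against a fixed 28 days, so full doses given on schedule can score well below 100%

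*SAP*

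**What the plan says.** SAP section 4.4.4 builds the measure in three steps.

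- Cumulative dose of each agent is a sum in mg/m²: "Cumulative chemotherapy administration will be calculated separately for Induction and Consolidation".
- Actual dose intensity is formed for each agent by phase "and treatment cycle (as the cumulative dose / duration".
- The last step is "Relative dose is set to 100*(Actual Dose Intensity/ (Expected Cumulative Dose / 28".

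The same section defines days on study medication, on study treatment and on study. None of these is the time covered by a chemotherapy cycle or phase. I found no definition of duration or of expected cumulative dose in either document.

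SAP section 6.3 asks for relative dose intensity of each agent "separately for Induction and Consolidation and presented by cycle and overall", next to "the number of chemotherapy cycles completed". The exposure table remains in the output list after termination (SAP section 10, Table 3).

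On schedule, SAP Table 2 plans consolidation cytarabine "BID over 3 hours on Days 1, 3 and 5 every 28-35 days for up to 3 cycles", and protocol Table 5 gives the same interval. Induction has up to two cycles and no stated cycle length. The nearest limit is on the marrow: "Subjects will undergo bone marrow examination no later than Day 42 of Induction Cycle 1 for assessment of response". Planned induction cytarabine (SAP Table 1) is 100 mg/m² "by continuous infusion, Days 1-7" in Cycle 1, and 1.0 g/m² twice daily on Days 1 to 6 in Cycle 2.

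**The concern.** A relative dose intensity should be 100% when the planned dose is given on the planned schedule. That requires the time in the numerator and the time in the denominator to describe the same stretch of treatment. Here the numerator time is left open and the denominator time is always 28 days, for every agent, cycle and phase.

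The plan's own schedule does not fit one constant. Consolidation cycles may last 28 to 35 days, induction cycles have no set length, and both phases can contain several cycles. A fall in the score when treatment is delayed beyond the plan is what a time-adjusted intensity is meant to show. A fall inside the permitted interval is different, because a reader of the study report could take an on-schedule course for under-dosing. At phase level, one unscaled 28 may be set against the dose and time of two or three cycles.

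**Working it through.** The SAP states no value of relative dose intensity (RDI), so there is no figure to reproduce. I applied its formula to full planned doses under the possible readings.

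**Formula** (SAP 4.4.4): RDI = 100 × (A/D) / (E/28), where A is the dose given, E the expected dose and D the duration in days.

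**Dose inputs**
- Consolidation cytarabine, under 60 years (SAP Table 2): 3.0 × 2 × 3 = 18 g/m² per cycle. At 60 or over: 1.5 × 2 × 3 = 9 g/m². The dose cancels, so the percentages are the same.
- Induction cytarabine (SAP Table 1): Cycle 1, 100 × 7 = 700 mg/m²; Cycle 2, 1,000 × 2 × 6 = 12,000 mg/m²; together 12,700 mg/m².

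**Step 1: one cycle at full dose.** With A = E, RDI = 100 × 28/D.

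| Reading of duration | D (days) | RDI |
|---|---|---|
| Nominal cycle length | 28 | 100% |
| Elapsed, shortest permitted consolidation | 28 | 100% |
| Elapsed, midpoint | 31.5 | 88.9% |
| Elapsed, longest permitted consolidation | 35 | 80.0% |
| Elapsed, marrow examined on Day 42 | at least 41 | at most 68.3% |
| Dosing days, Induction Cycle 1 cytarabine | 7 | 400% |
| Dosing days, consolidation cytarabine | 3 | 933.3% |

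The Day 42 row assumes that the next cycle starts on or after the marrow examination. It applies to Induction Cycle 1. It also applies to Consolidation Cycle 1 when that cycle serves as Chemotherapy Cycle 2, because SAP section 2.1 allows that marrow up to Day 42 as well.

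For comparison, a 20% dose cut over 28 days has A = 0.8E and D = 28, so RDI = 80.0%. It cannot be told apart from full dose at 35 days.

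**Step 2: overall consolidation, elapsed time.** For n full cycles of L days, A = 18n and D = nL.
- E as phase total (18n): RDI = 100 × 28/(nL). Two 28-day cycles: 28/56 = 50.0%. Three 28-day cycles: 28/84 = 33.3%. Three 35-day cycles: 28/105 = 26.7%.
- E as one cycle (18): RDI = 100 × 28/L. Three 28-day cycles: 100%. Three 35-day cycles: 80%.

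**Step 3: overall induction cytarabine.** Take both cycles at full dose and, purely for illustration, 28 days each. Then A/D = 12,700/56 = 226.8 mg/m² per day.
- E = 12,700 (phase total): E/28 = 453.6, RDI = 50.0%.
- E = 700 (Cycle 1): E/28 = 25, RDI = 907.1%.
- E = 12,000 (Cycle 2): E/28 = 428.6, RDI = 52.9%.

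Neither cycle's planned dose gives 100%. Only the average of the two, 6,350 mg/m², would, and the SAP mentions no such average.

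**The case against.** The case on the other side is substantial. The SAP prints no relative dose intensity, so nothing in it has been miscalculated, and every percentage above depends on an assumed meaning of duration. Twenty-eight days is the lower end of the planned interval; using the shortest interval as a fixed reference is a defensible convention, and longer cycles then score lower by design. A divisor of 28 pairs naturally with one cycle's expected dose, so the 33.3% needs a mismatched pairing. The formula is the same in both arms, and dosing listing 5.1 and the count of completed cycles do not depend on it.

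Most of this stands, and it sets the size of the point. It does not close the gap. The convention is not stated. A one-cycle expected dose rescues overall consolidation but not two-cycle induction. A nominal 28-day duration gives 100% for a full cycle, but the two 28s cancel and only a dose ratio is left. Independent programming (SAP Appendix A) may expose two readings, but the SAP has no rule to choose between them, and two programmers who share a reading would see no discrepancy.

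A reader might infer three stronger things that the documents do not support:
- That the report will show 33.3% for a complete course. This needs both elapsed time and a phase-total expected dose. The phase-level cumulative dose suggests the second, but the SAP does not state it.
- That averaging the cycle scores is an equally valid route to the overall value. The SAP defines intensity by phase from a phase-level cumulative dose, which points to pooling.
- That the comparison of arms or the safety conclusions are compromised. No inference is planned (SAP 4.4.3), and this is a single exposure statistic for background chemotherapy.

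**Conclusion.** The definition is incomplete, and on its natural elapsed-time reading it conflicts with the plan's own schedule. On that reading, full-dose consolidation cycles within the permitted interval score from 100% down to 80%, and a full-dose cycle with its marrow on Day 42 scores at most 68.3%. The overall consolidation value for three full 28-day cycles is 33.3% or 100%, depending on whether the expected dose is the phase total or one cycle. For two-cycle induction, neither cycle's planned cytarabine dose works as the expected dose.

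This rests on duration meaning elapsed time and, for the Day 42 figure, on the next cycle starting no earlier than the marrow examination. Severity is minor: one descriptive table (Table 3), 15 randomized subjects (SAP 4.2) and no inference. It is still worth correcting, because SAP section 6.3 keeps the statistic among the outputs to be produced.

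**What to change.** Replace the definition, for both Induction and Consolidation, with a dose ratio per agent: 100 × cumulative dose given / cumulative dose planned, over the cycles started. Planned dose is the SAP Table 1 or Table 2 dose for the subject's age group before any reduction. Give it by cycle, and pool doses for the overall row. Leave the ratio blank for a cycle in which no dose of that agent is planned, such as anthracycline in Induction Cycle 2 at 60 or over. Summarise actual cycle length, Day 1 to the next Day 1, as a separate line; the last cycle has no next Day 1 and contributes only to the dose ratio.

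Three full consolidation cycles then give 54/54 = 100% whether they last 28 or 35 days, and a 20% cut in one cycle gives 14.4/18 = 80%. Full two-cycle induction gives 12,700/12,700 = 100%. Early stopping remains visible in the number of cycles completed, which section 6.3 already tabulates. The small downside is that the ratio does not reflect delay; the cycle-length line does.

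If a time-adjusted intensity is preferred, define duration, make numerator and denominator cover the same cycles, sum the reference time over the cycles started, and state a rule for the last cycle. Limiting the reference to 35 days would not be enough: a full-dose Consolidation Cycle 1 given as Chemotherapy Cycle 2, with marrow on Day 42, would still score at most 35/41 = 85.4%.

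The cost is one SAP definition and a small programming change before database lock. The IV administration data are already collected and listed. No dose or clinical schedule is changed.
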